The generation of knowledge regarding the usefulness of metformin in this specific group of patients can lay the groundwork for research on the effect of this drug in solid tumors and other pediatric neoplasms.

HYPOTHESIS

If metformin is added to standard chemotherapy during the remission induction phase in Mexican adolescents with newly diagnosed ALL, then it will decrease the level of ABCB1/MDR1 gene mRNA expression and increase AMPK expression levels, at the end of this treatment period.

OBJECTIVES

General:

- To evaluate the efficacy of metformin in modifying ABCB1 and AMPK gene expression in adolescents diagnosed with ALL during the remission induction phase.

Specific

- To describe the expression levels of ABCB1/MDR1 and AMPK genes in adolescents with ALL at diagnosis and in healthy controls.
- To compare the expression levels of ABCB1/MDR1 and AMPK genes at diagnosis and at the end of induction in adolescents with ALL treated with conventional chemotherapy and those additionally treated with metformin.
- To compare overall and disease-free survival in adolescents with ALL treated in relation to ABCB1/MDR1, and AMPK gene expression.
- To compare overall and disease-free survival in adolescents with ALL treated with conventional chemotherapy with those treated with conventional chemotherapy plus metformin.

METHODOLOGY

Type and design of study

Type of study: randomized clinical trial

Study design: analytical, experimental, longitudinal and prospective study.

Population

The population to be studied are patients with newly diagnosed ALL between 10 and 21 years.

Eligible population: patients with newly diagnosed ALL between 10 and 21 years old, diagnosed at the Hospital General de México "[name]" from February 2021 to December 2023.

Inclusion, exclusion and elimination criteria

- Inclusion criteria:
 1. Patients aged between 10 and 21 years with a new diagnosis of ALL at the Hospital General de México, [name].
 2. Patients and legally authorized person who sign the informed consent.

- Exclusion criteria:
 1. Patients with antineoplastic treatment prior to admission.
 2. Patients with Down syndrome.

- Elimination criteria:
 1. Patients who abandon treatment for more than a few weeks.4
 2. Patients who withdraw informed consent

Sample size

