To calculate the sample size, we used data from the publication by Ramos Peñafiel⁶³, where a decrease in the expression pattern of ABCB1 gene expression from high to low expression after metformin administration was 50%.

The sample size calculation was based on the formula for estimating a proportion, with a confidence level of 95% and a precision of 5%:

$$n = \frac{Z_{\alpha}^2 * p * q}{d^2}$$

A sample number of 8 patients in each group is obtained, assuming a loss of 20%, 10 patients are calculated for each group.

Definition of the variables to be evaluated and how they are to be measured

Variable	Conceptual Definition	Unit of measurement	Type of variable	Coding
Age	Time elapsed in years since birth.	Years	Quantitative	Not applicable

Gender	Male or female phenotype of the person.	Male/female	Qualitative Dichotomous	0: male 1: female
Leukocyte count at diagnosis	Number of total leukocytes reported on complete blood count at diagnosis.	X10/ml ³	Quantitative	Not applicable
Hemoglobin at diagnosis	Measurement of the amount of oxygen transport protein reported in initial complete blood count.	g/dL	Quantitative	Not applicable
Platelet count at diagnosis	Measurement of the number of platelet fragments produced by the megakaryocytes, reported in the initial complete blood count.	X10/ml ³	Quantitative	Not applicable
Immunophenotype of leukemia lymphoblastic	Cellular variant of acute lymphoblastic leukemia	B/ T	Qualitative dichotomous	0: strain B 1: lineage T
Cytogenetic alterations	Alterations in the genetic structure of leukemic cells.	None/ t(9;22)/ t(12,21)/ t(4,11), other	Qualitative polytomous	0: none 1: t(9;22), 2: t(12,21) , 3: t(4,11), 4: other
MDR-1 and AMPK gene expression.	Amplification of gene expression by RT-PCR	No expression / low expression / high expression expression	Qualitative polytomous	0: not expressed 1: high expression 2 low expression
Pre-phase response with prednisone	Decrease in total peripheral blood blast count less than 1000 after 7 days of steroid (day 0)	Present/absent	Qualitative dichotomous	0: Yes 1: No
Morphological status at day +14	Presence of blasts in bone marrow sample per day +14 referral induction	M1, M2, M3	Qualitative polytomous	0: M1 1: M2 2: M3
Morphological response at the end of induction	Presence of blasts in the bone marrow aspirate at the completion of remission induction phase.	M1, M2, M3	Qualitative polytomous	0: M1 1: M2 2: M3

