Minimal residual disease at the end of induction.	Flow cytometry measurement of the presence of 1x10 ⁻³ blasts.	Positive /Negative	Qualitative dichotomous	0: positive 1: negative
Relapse	Presence of blasts in bone marrow after remission has been achieved.	Present/absent	Qualitative dichotomous	0: absent 1: present

Time to relapse	Time from diagnosis of leukemia to relapse	Days	Quantitative	Not applicable
Death	Cessation of life	Present/absent	Qualitative dichotomous	0: absent 1: present
Time to death	Time from leukemia diagnosis to death	Days	Quantitative	Not applicable

Table 1. Variable definitions.

PROCEDURES

Patients with a newly morphological diagnosis of ALL at the Hospital General de México "[name]" will be invited to participate in this trial, and informed consent will be requested from parents and participants.

The data collection is obtained from the patients chart such as age, gender, leukocyte count, hemoglobin, platelet count and immunophenotype.

Peripheral blood samples will be collected in EDTA tube. The sample will be centrifuged obtaining mononuclear cells, and the analysis of ABCB1 and AMPK expression will be performed. This will be done on samples obtained before the start of treatment and at the end of the induction phase. Samples will be collected by peripheral vein puncture, and mononuclear cells will be separated using density gradient. Mononuclear cells are separated and suspended in PBS medium and stored at -70°C . RNA isolation is performed using TRIzol® (Invitrogen/life Technologies), and will be stored at -80°C until use. For cDNA synthesis, 2g of RNA, final volume of 20L will be combined with 200U of MMLV RT enzyme (Invitrogen, Carlsbad, CA, USA).

Expression of mRNA levels will be measured using the TaqMan gene expression assay (Applied Biosystems Foster city, CA, USA). The cut-off point between low and high expression will be determined according to mean values obtained in healthy controls, selected during case recruitment in a 2:1 ratio for each case.

Regarding treatment, patients will be randomized into 2 groups, where in both cases the conventional remission induction treatment will be given, and to intervention group metformin will be added at a dose of 1000mgm2Seday, divided into two doses, with a maximum dose of 850mg every 8 hour, orally.

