The Kolmogorov-Smirnov test will be performed for continuous variables to determine if they have normal distribution; if they have normal distribution, both groups will be analyzed by means of the t-student test; if they do not have normal distribution, the chi-square test, Fisher's exact test and Mann Whitney U test will be used for the bivariate analysis. To compare the expression of ABCB1/MDR1 and AMPK genes at the time of diagnosis and at the end of induction, McNemar's test will be used.

For the calculation of the overall and disease-free survival function, the Kaplan Meier survival test will be used for both groups and the differences between groups will be analyzed by means of the log Rank test, both for overall and disease-free survival. Similarly, the overall and disease-free survival function will be analyzed with the Kaplan Meier test and log rank for ABCB1/MDR1 and AMPK gene expression.

ETHICAL AND BIOSAFETY ASPECTS

According to the General Health Law regarding research on human subjects, this protocol is considered a higher than minimal risk research, since randomized methods of assignment to therapeutic schemes are used.

This protocol takes into account the Mexican General Health Law regarding the provision of health care services and health research, as well as national and international ethical standards.

This study will be carried out with strict observance of recognized scientific principles and respect and confidential handling of the data obtained. The security mechanisms to maintain the ethical aspects of this study are:

1. Review of this protocol by the research and ethics committees of the Hospital General de México "[name]".
2. All information obtained in this study will be made available to the Ethics and Research Committees.
3. The confidentiality of the study information is assured, as well as the identity of the patients. The identification data of the participants will be codified, assigning a consecutive participation number. The identification information and the relation between the identification numbers and the data obtained will be known only to the participating investigators and will be preserved confidentially in electronic media.
4. There will be no charge for the study, nor will there be any consistency for participation in this study. Refusal to participate in the study will not influence the patient's treatment or clinical care.

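### Tests are not assigned by variable type, a normality pre-test picks among them, and no between-arm analysis of gene expression is named

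*Combined protocol and SAP*

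**What the plan says.** Four places in the combined protocol and SAP bear on this.

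- **Statistical Analysis, choice of test.** "The Kolmogorov-Smirnov test will be performed for continuous variables to determine if they have normal distribution". If they do, the groups are compared by Student's t-test; "if they do not have normal distribution, the chi-square test, Fisher's exact test and Mann Whitney U test will be used". The section gives no significance level for the pre-test, does not say whether it is run by arm or pooled, and does not say whether the Lilliefors correction applies.
- **Statistical Analysis, gene expression.** For the comparison of expression at diagnosis and "at the end of induction, McNemar's test will be used". No other test is named for expression, apart from its use as a grouping factor in the survival analyses.
- **Table 1 and Procedures.** Expression is declared a qualitative variable with three levels, coded "0: not expressed 1: high expression 2 low expression". "The cut-off point between low and high expression will be determined according to mean values obtained in healthy controls". The underlying measurement is a TaqMan mRNA level, so a quantitative value exists for each sample.
- **Hypothesis and Objectives.** The hypothesis is a change in expression levels when metformin is added. The second specific objective is "To compare the expression levels of ABCB1/MDR1 and AMPK genes at diagnosis and at the end of induction", in patients on conventional chemotherapy and in those also given metformin.

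**The concern.** Non-normality is a reason to use a rank test or a transformation. It is never a reason to use chi-square or Fisher, which need the variable to be cut into categories. As worded, the section leaves three tests open for a non-normal continuous variable, so the choice can be made after the data are seen.

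The larger gap is in the trial's own question. Metformin against control is a comparison between arms. McNemar's test is paired and works within patients. Run separately in each arm, it tests whether expression changed in that arm, not whether the change differs between arms. A reader looking for the between-arm test of expression finds only the test-selection sentence. If expression is taken as continuous, the pre-test governs. If it is taken as categorical, chi-square and Fisher are mentioned only as a consequence of non-normality. On either reading the central comparison is unspecified, in a trial of 8 to 10 patients per arm.

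**Working it through.** **Inputs from the documents.** 8 evaluable and 10 enrolled per arm (Sample size): 8 / (1 − 0.2) = 10. The plan states no power for a between-arm comparison of expression, so there is no figure of its own to reproduce. (That 8 does not follow from the stated precision formula is a separate matter: 1.96² × 0.5 × 0.5 / 0.05² = 384.2, rounded up to 385. The 8 and 10 are used here only as the planned group sizes.)

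**Assumptions, because the documents give no distribution, SD or effect.** Log-normal expression, log-SD 0.5 to 1.5, two-sided 5% level for both the pre-test and the comparison. The rule is read as Mann-Whitney if either arm fails the pre-test, otherwise a t-test on raw values. All power figures are simulated.

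**Step 1: how often the pre-test flags skew, n = 10.** The 5% critical value of the statistic is 0.409 for the uncorrected test and 0.263 with the Lilliefors correction.

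| log-SD | uncorrected, one arm | uncorrected, either arm | Lilliefors, one arm | Lilliefors, either arm |
|---|---|---|---|---|
| 0.5 | 0.2% | 0.3% | 18% | 32% |
| 0.75 | 0.8% | 1.7% | 32% | 53% |
| 1.0 | 2.8% | 5.5% | 46% | 71% |
| 1.5 | 10.7% | 20% | 68% | 90% |

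**Step 2: what the pre-test costs against Mann-Whitney throughout.** The shift is 1.4 log-SDs, which puts Mann-Whitney at about 80% with 10 per arm. The fold difference is exp(1.4 × log-SD).

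| log-SD | fold difference | loss, uncorrected | loss, Lilliefors |
|---|---|---|---|
| 0.5 | exp(0.70) = 2.0 | 2 points (0 to 2) | about 0 |
| 0.75 | exp(1.05) = 2.9 | 8 points | about 0 |
| 1.0 | exp(1.40) = 4.1 | 16 points | about 0 |
| 1.5 | exp(2.10) = 8.2 | 27 points | about 0 |

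With 8 evaluable per arm and log-SD 1.0, Mann-Whitney has 71%, the rule 50% with the uncorrected test and 70% with Lilliefors, and a log-scale t-test 74%.

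**Step 3: what dichotomising costs.** Log-SD 1, 4-fold difference (ln 4 = 1.386), 10 per arm: log-scale t-test 83%, Mann-Whitney 80%, Fisher after a split at the pooled median 56%. The loss against Mann-Whitney is 80 − 56 = 24 points. With a fixed cut midway between the arms and a shift of 1.4, Fisher has 46% and chi-square 65%, losses of 34 and 15 points. Neither cut is the plan's: its cut-off is the healthy-control mean, and where that falls among patients is unknown. This loss hardly depends on log-SD, because ranks and categories do not change under a log transformation.

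**Step 4: what is named for the between-arm question.** McNemar's test uses pairs of binary values within patients, so treatment arm does not enter it. Table 1 has three expression levels, and the plan does not say how they collapse to two.

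**The case against.** The strongest reply is that the pre-test rule does not apply to gene expression. Table 1 calls expression qualitative, Procedures sets a high/low cut-off, the sample size rests on the proportion moving from high to low, and expression has its own sentence in Statistical Analysis. On those definitions the rule reaches mainly baseline descriptors such as age and blood counts, since times to relapse and death go to Kaplan-Meier and log-rank. Mann-Whitney is also in the same list, and because Table 1 labels every variable by type, the intended mapping can be guessed.

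Much of this stands. It rules out two stronger readings that a reader might infer:

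- That the plan definitely sends non-normal continuous data to chi-square or Fisher. It permits this but does not require it; the defect is a missing mapping.
- That the pre-test rarely detects skew, and so drains power from the expression comparison. This is true only of the uncorrected test. The documents do not say which version will be used, nor that expression will be analysed as a raw-scale continuous value.

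What the reply does not answer is the between-arm question. Treating expression as categorical leaves McNemar's test as its only named analysis, and that test does not compare arms.

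**Conclusion.** The point holds in a limited form. Two defects are plain from the text and need no assumptions: tests are not assigned by variable type, and no between-arm analysis of expression is named although the hypothesis and second specific objective call for one.

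The power cost of the pre-test is conditional. It runs from about zero (Lilliefors correction, mild skew or log-scale values) to 27 points (uncorrected test, raw scale, log-SD 1.5). At log-SD 1, dichotomising costs about 24 points with Fisher after a median split, more than the 16 points from the uncorrected pre-test; at log-SD 1.5 the two are similar. All of these figures rest on assumed log-normal data and assumed effects, so they show what could be lost, not what this trial will lose.

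**What to change.** Replace the test-selection sentence with a rule by variable type, without a normality pre-test, and add one main expression analysis. Suggested content:

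> Quantitative variables are compared between arms with the Mann-Whitney U test. Qualitative variables are compared with the chi-square test, or Fisher's exact test when expected counts are small. The main analysis of ABCB1/MDR1 and of AMPK compares end-of-induction log relative expression between arms in a linear model with baseline log relative expression as covariate. High/low categories and McNemar's test within each arm are secondary and descriptive.

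Three consequential edits keep the document consistent: add continuous relative expression to Table 1 beside the existing categories, state how three categories become two for McNemar's test, and state how samples with no detectable expression enter the log-scale analysis.

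Cost: one paragraph and one table row. No new data are needed, because expression is already measured at diagnosis and at the end of induction. Mann-Whitney gives up a few points of power if a variable is truly normal. The covariate costs one degree of freedom (20 − 3 = 17 residual, against 20 − 2 = 18, at 10 per arm). The rule for undetectable expression must be fixed before the data are seen.

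### The randomised question is metformin's effect on ABCB1/MDR1 and AMPK expression, but the only test assigned to expression as an outcome is a before/after McNemar test with no arm stated

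*Combined protocol and SAP*

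**What the plan says.** The general objective is "To evaluate the efficacy of metformin in modifying ABCB1 and AMPK gene expression in adolescents diagnosed with ALL" during remission induction. The Hypothesis section says that if metformin is added to standard chemotherapy, "it will decrease the level of ABCB1/MDR1 gene mRNA expression and increase AMPK expression levels" by the end of that period. The second specific objective compares expression at diagnosis and at the end of induction in "adolescents with ALL treated with conventional chemotherapy and those additionally treated with metformin". Under Procedures, patients are randomised into two groups. Both receive conventional induction, and one also receives metformin.

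The Statistical Analysis section contains four relevant statements:

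- **Generic tests.** Continuous variables are checked for normality. If normal, the two groups are compared by t test. If not, chi-square, Fisher and Mann-Whitney tests are used for bivariate analysis. No outcome is named.
- **Expression as an outcome.** For the two genes "at the time of diagnosis and at the end of induction, McNemar's test will be used". No arm is named.
- **Survival by arm.** Overall and disease-free survival are compared between groups by log-rank.
- **Survival by expression.** Kaplan-Meier and log-rank are repeated with gene expression as the grouping factor.

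Table 1 records expression in three categories: "No expression / low expression / high expression expression". Procedures adds: "The cut-off point between low and high expression will be determined according to mean values obtained in healthy controls". On sample size: "A sample number of 8 patients in each group is obtained", raised to 10 for losses.

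**The concern.** The objective, the hypothesis and the randomisation all pose a question of metformin against control. The one rule written for expression compares two time points instead. Between those time points every patient receives steroid and multi-agent chemotherapy, which could itself change expression in circulating mononuclear cells. Only the control arm can separate that change from a metformin effect, and McNemar's test in the metformin arm uses no control data.

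An analyst who follows the written rule could therefore report a significant before/after change, or a change significant with metformin but not in control, as support for the hypothesis. Neither is a test of metformin. This concerns the trial's general objective, not a secondary result.

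**Working it through.** **1. Which test goes with which outcome**

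| Outcome | Between-arm test assigned? | Other test assigned |
|---|---|---|
| Overall and disease-free survival | Yes, log-rank | Log-rank by expression |
| ABCB1/MDR1 and AMPK expression | None named | McNemar, diagnosis v end of induction, arm not stated |
| Unnamed continuous variables | t, or Mann-Whitney / chi-square / Fisher if non-normal | – |

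The only between-arm test tied to a named outcome is log-rank, for survival.

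**2. Inputs**

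- Group size: 8 evaluable, 10 planned (Sample size). The step for losses reproduces: 8/0.8 = 10. The 8 itself does not follow from the stated formula (1.96² × 0.5 × 0.5 / 0.05² ≈ 384). That is a separate matter; 8 and 10 are used here only as the planned numbers.
- Switch rate: the Sample size section cites a decrease "from high to low expression after metformin administration was 50"%, for ABCB1. No control rate and no AMPK rate is given.
- Assumed, because the documents do not give them: the share high at baseline, the rate of rises, the control switch rate, and two-sided alpha of 0.05.

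**3. How McNemar behaves at this size**

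With k falls and no rises, exact two-sided p = 2 × (1/2)^k. So k = 5 gives 0.0625 and k = 6 gives 0.031: at least six one-way switches are needed.

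Constructed example (it shows the pattern, not its likelihood): 6/8 on metformin and 5/8 on control fall, none rise. McNemar gives p = 0.031 and p = 0.063. Between arms, Fisher gives p = 1.00, with a difference of 75% − 62.5% = 12.5 points (Newcombe 95% CI −29 to +49).

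**4. Rejection when metformin does nothing**

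Assume 50% of high patients fall in both arms. With all high at baseline and none rising:

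- Metformin arm, n=8: P(X ≥ 6) = 37/256 = 14.5%.
- Metformin arm, n=10: P(X ≥ 6) = 386/1024 = 37.7%.
- Pooled, n=16: 1 − 6885/65536 = 89.5%.
- Pooled, n=20: 1 − 21700/1048576 = 97.9%.
- Fisher between arms, by enumeration: 2.1% (8 per arm), 1.3% (10 per arm).

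Varying the assumed mix (fall = share high × 0.50; rise = share low × rise rate):

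| Assumed mix | Fall / rise | McNemar, metformin arm, n=8 / 10 | McNemar pooled, n=16 / 20 | Fisher between arms, 8 / 10 per arm |
|---|---|---|---|---|
| All high, none rise | 0.50 / 0 | 14.5% / 37.7% | 89% / 98% | 2.1% / 1.3% |
| 70% high, none rise | 0.35 / 0 | 2.5% / 9.5% | 51% / 75% | 1.6% / 1.3% |
| 70% high, 30% of low rise | 0.35 / 0.09 | 1.9% / 5.6% | 20% / 30% | 1.6% / 1.3% |
| 50% high, 30% of low rise | 0.25 / 0.15 | 0.3% / 0.9% | 3.5% / 5.0% | 0.8% / 1.0% |

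The McNemar rate depends strongly on the mix and on pooling. The mix cannot be known in advance, because the cut-off is set from healthy controls.

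**5. Power of the between-arm test**

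Fisher, all high at baseline, 50% on metformin against an assumed control rate:

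| Control rate | 8 per arm | 10 per arm |
|---|---|---|
| 0% | 36% | 62% |
| 10% | 22% | 30% |
| 20% | 12% | 13% |
| 30% | 6% | 5.5% |

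At 50% v 10%, power first reaches 80% at about 23 per arm (81%; 79% at 22).

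**The case against.** The strongest defence is that the plan under-specifies the comparison rather than leaving it out. The generic sentence speaks of both groups and lists chi-square and Fisher, Table 1 classes expression as qualitative, and the second specific objective names both arms. A fair reader could take those tests to cover every Table 1 variable by arm, with McNemar added for the paired time points. This stands in part: a reader might infer that no between-arm test of expression could be run under the plan, and the text does not support that. But the sentence makes chi-square and Fisher depend on non-normality of continuous variables, and it names no outcome, time point or change measure. Survival, in the same section, gets an explicit between-group test. The second specific objective can also be read as before/after within each group, but that alone would not serve the general objective.

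The harm is also conditional. The 89% and 98% figures need pooling, all patients high at baseline and no rises, all at once. Sizing each group separately fits per-arm use better than pooling. Per-arm rates exceed 10% only in the all-high case. These objections stand.

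The three-category coding is secondary: McNemar's test has an extension to more than two categories, and Procedures does define a low/high cut-off. A collapsing rule is a clarification.

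**Conclusion.** The point holds and should be fixed before analysis. The rule written for expression cannot answer the general objective, and no other test is tied to that outcome. This rests on the text and on one fact that no assumption alters: McNemar in the metformin arm gives the same result whatever happens in the controls.

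The size of the risk is illustrative only. With no metformin effect, the per-arm rejection rate runs from 0.3% to 38% over the mixes tried, and the pooled rate from 3.5% to 98%. A reader might infer that the planned analysis has a false-positive rate near 90%. The documents do not support that, because they give no baseline share, reverse rate, control rate or instruction to pool.

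A reader might also infer that the pattern of significance with metformin only never separates effect from no effect. That is too strong. With all high and 10 per arm, it occurs in 37.7% of trials when the control rate is 10% and in 23.5% when it is 50%. At 8 per arm the figures are nearly equal (14.5% v 12.4%).

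**What to change.** In the Statistical Analysis section, make the between-arm comparison the primary analysis of expression for each gene:

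- Fisher's exact test by randomised arm, with the arm difference and 95% CI.
- One stated measure: either the target category at end of induction (low or not expressed for ABCB1, high for AMPK) or the proportion changing category.
- The denominator for that measure, for example all randomised patients with an end-of-induction sample, or only those able to change.
- A rule for collapsing the three Table 1 categories to two.
- McNemar kept as a per-arm description only.

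An order for the two genes and a baseline-adjusted analysis of the continuous TaqMan level are optional. Whether the end-of-induction sample is blood or marrow is a separate point.

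The cost is a few sentences, with no new visits, samples or assays. The downside is low power: 22% with 8 per arm or 30% with 10 at 50% v an assumed 10%, all high at baseline. The choice of measure matters too. If 70% are high and none rise, low expression at end of induction is 0.30 + 0.70 × 0.50 = 65% v 0.30 + 0.70 × 0.10 = 37%, with power of 12% or 10%. The proportion changing among all evaluable is 35% v 7%, with power of 7% or 13%. Results should therefore be presented as estimates with intervals. For example, 5/10 v 1/10 is a difference of 40 points, 95% CI about 0 to 68, Fisher p = 0.14. Low power is not a reason to fall back on a test that does not address metformin.

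### The trial is sized on estimating a proportion with 95% confidence, but no between-arm effect estimate or interval is planned, even for the hypothesised difference in expression change

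*Combined protocol and SAP*

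**What the plan says.** **Sample size.** The planning figure comes from a cited study in which "a decrease in the expression pattern of ABCB1 gene expression from high to low expression" was seen in 50% of cases after metformin. The calculation uses the "formula for estimating a proportion, with a confidence level of 95% and a precision of 5" per cent. The stated result is: "A sample number of 8 patients in each group is obtained, assuming a loss of 20%, 10 patients are calculated for each group". No power, test level, control-arm rate or between-arm difference is given.

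**Hypothesis and Objectives.** The hypothesis is that adding metformin to induction lowers ABCB1/MDR1 expression and raises AMPK expression by the end of induction. One specific objective compares expression at diagnosis and at end of induction between patients with and without metformin. Another compares overall and disease-free survival between the same groups.

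**Statistical Analysis.** The plan has three parts:
- descriptive summaries (percentages, counts, medians, ranges, means, standard deviations);
- a normality check leading to t, chi-square, Fisher or Mann-Whitney tests, with McNemar's test for expression at diagnosis against end of induction;
- Kaplan-Meier curves for overall and disease-free survival, where "differences between groups will be analyzed by means of the log Rank test".

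No confidence interval, risk difference, hazard ratio or other between-arm effect measure appears. The only mention of 95% confidence is in the sample-size paragraph.

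**The concern.** The sample-size paragraph treats the trial as an estimation exercise, but the analysis never returns to that quantity. The share of patients moving from high to low expression is not defined as an output, and no interval is attached to it.

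The gap matters most for the main question. McNemar's test asks whether expression changes between two time points in the same patients. Both arms receive chemotherapy, so a within-arm change can occur without metformin. The hypothesis concerns the difference between arms in that change. No test is explicitly assigned to that difference, and no estimate of it is planned.

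With about 10 patients per arm, a p-value without an effect size and interval cannot separate little or no effect from too little information. The trial could meet its plan in full and still not report how large a metformin effect its data are compatible with.

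**Working it through.** **Inputs from the protocol.** Anticipated proportion after metformin p = 0.50; 95% confidence (Z = 1.96); precision d = 0.05; 8 per group, or 10 after allowing for 20% loss.

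**Assumed inputs.** The documents give no control-arm shift rate and no expected number of survival events. Control rates of 0%, 10% and 20% and totals of 4 to 12 events are used below as illustrations.

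**1. The protocol's own figure.** n = Z²pq/d² = 1.96² × 0.5 × 0.5 / 0.05² = 384.16, so 385 per group and not 8. The loss step does reproduce: 8 / (1 - 0.20) = 10. The 385 against 8 is a separate defect. It matters here only because it fixes the precision available: 1.96 × √(0.25/8) = 0.35 at 8 patients and 1.96 × √(0.25/10) = 0.31 at 10, against the stated 0.05.

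**2. One arm, exact (Clopper-Pearson) 95% interval.** 5/10 gives 18.7% to 81.3%; 4/8 gives 15.7% to 84.3%.

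**3. Power of Fisher's exact test between arms.** Two-sided 5%, true rate 50% with metformin, by enumeration of all outcomes:

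| Assumed control rate | 8 per arm | 10 per arm |
|---|---|---|
| 0% | 36% | 62% |
| 10% | 22% | 30% |
| 20% | 12% | 13% |

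**4. What a p-value alone would hide.** For 5/10 v 2/10, with 7 shifts among 20 patients, the two-sided Fisher p is 2 × (11,340 + 2,100 + 120) / 77,520 = 0.350. The Wilson limits are 0.237 to 0.763 for 5/10 and 0.057 to 0.510 for 2/10. Newcombe's interval for the difference of 0.30 is then:
- lower: 0.30 - √[(0.500 - 0.237)² + (0.510 - 0.200)²] = -0.107;
- upper: 0.30 + √[(0.763 - 0.500)² + (0.200 - 0.057)²] = 0.600.

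The same method for the three illustrative results:

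| Result | Fisher p | Difference | Newcombe 95% CI |
|---|---|---|---|
| 5/10 v 2/10 | 0.350 | 30 points | -10.7 to 60.0 |
| 5/10 v 1/10 | 0.141 | 40 points | -0.2 to 67.6 |
| 5/10 v 0/10 | 0.033 | 50 points | 11.7 to 76.3 |

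**5. The within-patient test.** Exact McNemar reaches p < 0.05 only with at least 6 discordant patients, if all change in one direction: 2 × 0.5⁶ = 0.031, whereas 2 × 0.5⁵ = 0.0625. If every patient starts high, half shift and none reverse, power within one arm is P(at least 6 shifts) = 14% at n = 8 and 38% at n = 10.

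**6. Survival.** At a hazard ratio of 0.5, log-rank power (Schoenfeld) is 10% with 4 events and 22% with 12. It is 34% even if all 20 patients had an event; 80% power needs 66 events. The 95% limits are the hazard ratio divided and multiplied by exp(1.96 × √(4/events)), which is 7.1 with 4 events and 3.1 with 12.

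**The case against.** **Point estimates are planned.** A reader might infer that the analysis consists only of significance tests. It does not. Percentages are planned for qualitative variables, the variable table classes gene expression as qualitative, and Kaplan-Meier estimates will be produced. This limits the point to between-arm effect measures and intervals, which are absent, and to the per-patient shift, which is not defined as an output.

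**Non-significance is not a foregone conclusion.** A reader might infer that most comparisons will be non-significant even if metformin works as planned. The documents do not support that. They give no control rate, so working as planned has no between-arm meaning. With a 0% control rate and 10 per arm, power is 62%, and 5/10 v 0/10 is significant.

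**The 50% is not a between-arm margin.** It is tempting to say that absence of effect may be concluded once an interval excludes a 50-point shift. The protocol's 50% is a rate in one group after metformin, not a difference between arms. Such a rule would also be unsafe: 5/10 v 5/10 gives -37 to +37 points, which excludes 50 while large effects remain possible.

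**No misreading is written into the plan.** Nothing in the protocol says that p > 0.05 will be taken as no effect. That risk is a prediction about how results may be read.

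**The small sample is the root problem.** Much of the practical consequence does come from the small number of patients. Intervals would show the imprecision, not remove it. That is a reason to report them.

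**Conclusion.** The point holds as a gap in the analysis plan that should be closed. The trial is sized on estimating a proportion, yet the plan specifies no between-arm effect estimate and no confidence interval. The hypothesised between-arm difference in expression change has neither an estimate nor an explicitly assigned test. That much follows from the text and needs no assumption.

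The size of the consequence does rest on assumptions. With 50% shifting under metformin and 10 per arm, Fisher power is 62%, 30% or 13% for control rates of 0%, 10% or 20%. At the two higher rates a non-significant result is more likely than not, and it could accompany an observed difference of 30 to 40 points. These figures take Fisher's test from the general list in the plan as the between-arm test, because none is named for this comparison. The survival figures assume 4 to 12 events and a hazard ratio of 0.5.

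**What to change.** Add to the Statistical Analysis section:

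1. For each gene, the proportion shifting category in each arm with an exact 95% CI, and the between-arm difference with a Newcombe 95% CI. State the direction of shift counted and the denominator.
2. For measured expression, the Hodges-Lehmann between-arm difference in change from diagnosis to end of induction, with 95% CI. The assay measures mRNA levels, so the measured values need to be kept alongside the high/low category.
3. For overall and disease-free survival, the between-arm difference in 12-month Kaplan-Meier estimates with 95% CI, labelled exploratory.
4. A statement that a non-significant result will not be read as absence of effect. If the sponsor wants to be able to conclude no relevant effect, it must set and justify a between-arm margin of its own, because the protocol supplies none.

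The cost is analysis wording and minor programming. No extra patients, samples or visits are needed. The sample-size arithmetic needs its own correction, which this change does not replace.
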